4.2. Extent of Study Drug Exposure and Adherence

Extent of exposure to study drug will be examined by assessing the total duration of exposure to study drug and the level of adherence to the study drug specified in the protocol.

4.2.1. Duration of Exposure to Study Drug

For each study phase, duration of exposure to study drug will be defined as last dosing date minus first dosing date plus 1 and then divided by 7, regardless of any temporary interruptions in study drug administration, and will be expressed in weeks using up to 1 decimal place (eg, 4.5 weeks). For the Randomized Phase, first dosing date is the earlier date between the 2 drug types; last dosing date is the later date between the 2 drug types. If the last study drug dosing date is missing, the latest date among the study drug end date, clinical visit date, laboratory sample collection date, and vital signs assessment date that occurred during the corresponding phase will

be used for the final analysis. At the time of an interim analysis, the missing last dosing date will be imputed by the data snapshot date (or data cut date, if applicable) for subjects who are still on treatment.

The duration of exposure to study drug will be summarized using descriptive statistics and the number (ie, cumulative counts) and percentage of subjects exposed through the following time periods: 1 day, 1 week, 4 weeks, 12 weeks, 24 weeks, 36 weeks, 48 weeks, and every 24 weeks thereafter. Summaries will be provided according to subject grouping defined in Section 3.2.

No formal statistical testing is planned.

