### 6.7. Open-Label Phase

Subjects who progress to cirrhosis on liver biopsy or experience a hepatic clinical event (refer to Section 3.2) prior to completing the Week 240 Visit of the Randomized Phase will be offered the option to rollover into an Open-Label (OL) Phase of the study. Each of the clinical events (except death and liver transplantation) will require confirmation by a Hepatic Events Adjudication Committee. All deaths will be reviewed by this committee to determine if they are liver-related.

Subjects who undergo liver transplantation are not eligible to participate in the OL Phase of the study and should discontinue from the study immediately. Subjects who have permanently discontinued study drugs are not eligible for the OL Phase of the study.

Once a clinical event (except histological progression to cirrhosis, death and liver transplantation) is confirmed by the Hepatic Events Adjudication Committee, the subject will no longer participate in the Randomized Phase and will be offered the option to receive SEL 18 mg in the OL Phase for a total treatment duration of 240 weeks inclusive of the Randomized Phase.

Rollover into the OL Phase of the study must occur within 60 days of confirmation of the event. Subjects starting the OL Phase of the study will complete the same study procedures as during the Randomized Phase of the study, CCI

. Hepatic clinical events will be adjudicated and deaths will be reviewed by the Hepatic Events/DILI Adjudication Committee only during the Randomized Phase of the study; potential DILI events and cardiovascular events including deaths will continue to be adjudicated in the OL Phase by the Hepatic Events/DILI Adjudication Committee and the Cardiovascular Events Adjudication Committee, respectively.

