#### **6.8. Criteria for Discontinuation of Study Treatment**

Study medication must be discontinued in the following instances:

- Subject who develops a serious adverse event consisting of a serious hypersensitivity reaction to study drug
- Intercurrent illness that would, in the judgment of the investigator, affect assessments of clinical status to a significant degree. Following resolution of intercurrent illness, the subject may resume study dosing at the discretion of the investigator
- Unacceptable toxicity or toxicity that, in the judgment of the investigator, compromises the ability to continue study-specific procedures or is considered to not be in the subject's best interest
- Subject or investigator request to discontinue for any reason
- Significant subject noncompliance
- Significant protocol violation that impacts subject safety
- Pregnancy during the study; refer to [Appendix 3](#)
- Discontinuation of the study at the request of Gilead, a regulatory agency or IRB/IEC/EC

Subjects who discontinue study treatment should be encouraged to complete study visits through Week 240, Follow-Up and a Telephone Follow-Up.

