3.8.2. Analysis Visit Windows

Subject visits might not occur on protocol-specified days. Therefore, for the purpose of analysis, observations will be assigned to analysis windows.

On-treatment visit windows will be calculated from Study Day 1/OL Study Day 1 for selected efficacy measures, vital signs, elastography, and safety laboratory data.

Selected safety and efficacy data, unless otherwise specified, collected up to and including the last dosing date in the Randomized Phase + 30 days and before OL Study Day 1 for the Randomized Phase, whichever is earlier, or OL last dosing date + 30 days for the OL Phase, will be mapped according to the following analysis windows unless the nominal visit name is Follow-Up or OL Follow-Up.

All biopsy data and elastography data collected will be mapped to Randomized Phase visit windows unless on or after OL Study Day 1. HRQoL questionnaires and HRUQ will not be windowed, and will be summarized by nominal visit. For those endpoints, missing (OL) Baseline/Day 1 values will not be imputed.

The analysis windows for select measures are provided in [Table 3-1](#) to [Table 3-6](#).

Table 3-1. Analysis Visit Windows for Chemistry, Hematology, Coagulation, CP/MELD scores, Vital Signs, Body Weight, and Stool Frequency

Analysis Visit	Nominal Day	Lower Limit	Upper Limit
Baseline/OL-Baseline	1	(none)	1
Week 1/OL-Week 1	8	2	18
Week 4/OL-Week 4	29	19	42
Week 8/OL-Week 8	57	43	70
Week 12/OL-Week 12	85	71	98
Week 16/OL-Week 16	113	99	126
Week 20/OL-Week 20	141	127	154
Week 24/OL-Week 24	169	155	182
Week 28/OL-Week 28	197	183	210
Week 32/OL-Week 32	225	211	238
Week 36/OL-Week 36	253	239	266
Week 40/OL-Week 40	281	267	294
Week 44/OL-Week 44	309	295	322
Week 48/OL-Week 48	337	323	378
Week 60/OL-Week 60	421	379	462
Week 72/OL-Week 72	505	463	546
Week 84/OL-Week 84	589	547	630
Week 96/OL-Week 96	673	631	714
Week 108/OL-Week 108	757	715	798
Week 120/OL-Week 120	841	799	882
Week 132/OL-Week 132	925	883	966
Week 144/OL-Week 144	1009	967	1050
Week 156/OL-Week 156	1093	1051	1134
Week 168/OL-Week 168	1177	1135	1218
Week 180/OL-Week 180	1261	1219	1302
Week 192/OL-Week 192	1345	1303	1386
Week 204/OL-Week 204	1429	1387	1470
Week 216/OL-Week 216	1513	1471	1554
Week 228/OL-Week 228	1597	1555	1638
Week 240/OL-Week 240	1681	1639	≥1681

Table 3-2. Analysis Visit Windows for Waist Circumference, Insulin, Homeostasis Model Assessment of Insulin Resistance (HOMA-IR), Lipids and Hemoglobin A1c

Analysis Visit	Nominal Day	Lower Limit	Upper Limit

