7.1.5. Treatment-Emergent Adverse Events

7.1.5.1. Definition of Treatment-Emergent Adverse Events

Treatment-emergent adverse events (TEAEs) for the Randomized/OL Phase are defined as 1 or both of the following:

- Any AEs with an onset date on or after the study drug start date and no later than 30 days after permanent discontinuation of study drug in the Randomized Phase (and before the first dosing date in the OL Phase)/ OL Phase.
- Any AEs leading to premature discontinuation of study drug in the Randomized/OL Phase.

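### SAP 4.2.1 imputes a missing last dosing date with no cap at drug discontinuation, which overstates exposure and stretches the last-dose + 30 days window for subjects who stop drug but stay on study

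*SAP*

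**What the plan says.** SAP 4.2.1 defines exposure as "last dosing date minus first dosing date plus 1 and then divided by 7", in weeks. For the final analysis it replaces a missing last dosing date with "the latest date among the study drug end date, clinical visit date, laboratory sample collection date, and vital signs assessment date", provided the date is one "that occurred during the corresponding phase". SAP 3.6.1 points to 4.2.1 as the rule for a missing last dosing date. At the Week 48 interim, a missing date becomes the snapshot or cut date, but only for subjects still on treatment.

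Protocol 6.8 states: "Subjects who discontinue study treatment should be encouraged to complete study visits through Week 240, Follow-Up and a Telephone Follow-Up". Protocol 6.7 states: "Subjects who have permanently discontinued study drugs are not eligible for the OL Phase of the study". The off-drug visits of permanent discontinuers therefore remain in the Randomized Phase.

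The last dosing date is then used in several places:
- SAP 4.2.2.1 takes expected tablets from the 4.2.1 duration.
- SAP 7.2.2.1, 7.2.2.2 and 7.2.3 close the laboratory windows 30 days after the last dose.
- SAP 3.8.2 maps selected safety and efficacy data "collected up to and including the last dosing date in the Randomized Phase + 30 days".
- SAP 7.1.5.3 uses last dose + 30 days for AEs with incomplete onset dates.

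The main TEAE definition in SAP 7.1.5.1 is worded differently: onset "no later than 30 days after permanent discontinuation of study drug in the Randomized Phase".

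**The concern.** Taking the latest recorded contact is reasonable for someone lost while still on drug. It is not reasonable for someone known to have stopped who keeps attending. For that subject the last contact says nothing about the last dose, and because the rule is a maximum, a recorded study drug end date would lose to any later visit. SAP 4.2.2 describes adherence over the subject's actual on-treatment period, but the imputed duration can include years off drug.

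Safety is the trial's only secondary objective. The affected subjects are all discontinuers. If stopping differs between arms, the errors in exposure, adherence and laboratory abnormality counts will differ between arms too.

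**Working it through.** The check is date arithmetic.

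**The plan's own figures.** The Week 240 nominal day is 240 × 7 + 1 = 1681, as in SAP Table 3-1. Maximum follow-up is 240 + 12 = 252 weeks, and 252 × 7 / 30.4375 = 57.95, i.e. the 58 months in SAP 3.6.1.

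**Inputs.** First dose is on day 1. A subject stopping at Week *s* has a true last dose on day 7*s*. The last recorded contact is the Week 240 visit (day 1681) or, if the Follow-Up visit four weeks later counts as within the phase, day 1709. The subject is fully adherent, one tablet per day of each type, until stopping.

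**Formulas.**
- True exposure = 7*s*/7 weeks. Imputed exposure = 1681/7 = 240.1 weeks, or 1709/7 = 244.1 weeks.
- Window end = last dose day + 30. With the imputed date this is day 1711 or day 1739.
- Computed adherence = 7*s*/1681, or 7*s*/1709.

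| Stop | True exposure (wk) | Overstatement (wk) | Correct window end (day) | Computed adherence |
|---|---|---|---|---|
| Week 12 | 12.0 | 228.1 to 232.1 | 114 | 5.0% to 4.9% |
| Week 24 | 24.0 | 216.1 to 220.1 | 198 | 10.0% to 9.8% |
| Week 48 | 48.0 | 192.1 to 196.1 | 366 | 20.0% to 19.7% |
| Week 96 | 96.0 | 144.1 to 148.1 | 702 | 40.0% to 39.3% |
| Week 144 | 144.0 | 96.1 to 100.1 | 1038 | 60.0% to 59.0% |
| Week 192 | 192.0 | 48.1 to 52.1 | 1374 | 80.0% to 78.6% |

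For the Week 24 stop, the window closes on day 1711 instead of day 198: 1513 days, or 216.1 weeks, too late.

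SAP 4.2.2.2 uses a lowest adherence category of under 75%. Since 0.75 × 1681 = 1260.75 days, or about 180 weeks, a fully adherent subject who stops before about Week 180 and attends to Week 240 falls into that category through the imputation alone.

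A subject who leaves the study promptly is affected much less. An ET visit up to 30 days after the last dose and a Follow-Up visit 28 days later add at most 58 days, or 8.3 weeks.

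**Arm level.** The documents do not give the share of subjects who would have a missing date and stay on study off drug. Assuming 0.5% to 5% of an arm, each overstated by 100 to 196 weeks, mean exposure rises by between 0.005 × 100 = 0.5 weeks and 0.05 × 196 = 9.8 weeks. In a 320-subject arm that is 1.6 to 16 subjects. These shares show scale only and are not estimates.

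**The case against.** The strongest objection is that the rule will rarely apply. It needs a missing last dosing date, and it governs only the final analysis. Dosing is recorded in the eCRF (Protocol 5.3), sites must document IMP end dates (Protocol 9.1.5), and the final analysis follows query resolution (SAP 2.3). The only in-trial figure is 3 of 425 treated subjects off drug, at a median of 11.9 weeks (Protocol 1.2.10.1), too early to say much. The 20% in the sample-size section is overall dropout and does not measure stopping drug while remaining on study. All of this stands. The documents also do not say how the study drug end date differs from the last dosing date, so the case where a recorded end date is overridden may be uncommon or may not arise.

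A reader might infer that every off-drug AE becomes treatment-emergent, and that the tables of events more than 30 days posttreatment stay empty until after Week 240. The documents do not establish that. SAP 7.1.5.1 and 7.1.5.2 run from permanent discontinuation of study drug, and nothing says that date is filled from the 4.2.1 imputation. Protocol 8.2.1.2 does use last dose + 30 days for treatment-emergent data, so the reading is arguable. It remains conditional except for AEs with incomplete onset dates.

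A reader might also infer that every off-drug laboratory abnormality is counted. SAP 7.2.2.1 requires a rise of at least 1 grade from baseline; any graded abnormality counts only where baseline is missing.

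Nor is a confirmatory result at risk. SAP 3.8.2 maps biopsy and elastography data without the last-dose limit, and EFS censoring in SAP 6.2.3 uses visit and AE onset dates. AEs are reported as counts and percentages of subjects, so inflated exposure does not enter an AE rate.

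**Conclusion.** The point holds as a gap in a data-handling rule. For a subject who stops drug, keeps attending and lacks a last dosing date, SAP 4.2.1 as written returns the wrong date. The error passes directly into exposure, adherence, the laboratory windows, the mapping of selected non-biopsy measures and the status of AEs with incomplete onset dates. It can reach four years or more per subject for an early stop and about one year for a Week 192 stop, assuming attendance to Week 240 or Follow-Up. The effect on an arm is unknown and probably small, because it depends on how often the date is missing. This is a worthwhile clarification of the safety analyses and does not threaten the efficacy conclusions.

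**What to change.** Amend SAP 4.2.1 as follows:
- Where permanent discontinuation of study drug is recorded and the last dosing date is missing, use the study drug end date linked to that discontinuation.
- If that end date is also missing, use the latest visit, laboratory or vital-sign date on or before the recorded discontinuation, capped at the last dispensing date plus the days' supply dispensed.
- Keep the current rule only for subjects with no record of stopping drug.

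The end date must be the one tied to permanent discontinuation. An end date from an earlier dosing record, for example before a temporary interruption, could understate exposure. The same wording could serve at the Week 48 interim, where the SAP gives no rule for a subject already off drug.

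The cost is about two sentences in the SAP and a small programming change. Disposition, dispensing and accountability data are already collected. Only an analysis convention changes.

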4.2.2. Adherence to Study Drug

The total number of tablets administered will be summarized using descriptive statistics.

The presumed total number of tablets administered to a subject will be determined by the data collected on the drug accountability eCRF using the following formula:

Total Number of Doses Administered =

$$\left(\sum \text{No. of Doses Dispensed} \right) - \left(\sum \text{No. of Doses Returned} \right)$$

The level of on-treatment adherence to study drug regimen will be determined by the total amount of study drug administered relative to the total amount of study drug expected to be administered in each treatment phase during a subject's actual on-treatment period based on the study drug regimen.

The level of on-treatment adherence will be expressed as a percentage using the following formula:

$$\text{On-Treatment Adherence (\%)} = \left(\frac{\text{Total Amount of Study Drug Administered}}{\text{Study Drug Expected to be Administered on Treatment}} \right) \times 100$$

4.2.2.1. Randomized Phase

Study drug expected to be administered will be calculated as treatment duration in days (one tablet per day for each drug type) as defined in Section 4.2.1. The adherence rates of SEL 18 mg tablet for SEL 18 mg treatment group and SEL 6 mg tablet for SEL 6 mg treatment group, and the average of the adherence rates between PTM 18 mg and PTM 6 mg tablets for placebo group will be summarized by treatment group (1, 2 and 4) as defined in Section 3.2.

4.2.2.2. Open-Label Phase

On-treatment adherence will be calculated for OL SEL 18 mg. Study drug expected to be administered will be calculated as treatment duration in days (1 tablet per day). Adherence rates will be summarized for the OL SEL 18 mg group as defined in Section 3.2.

At interim analyses, if the subject is ongoing, the number of tablets administered and expected to be administered on treatment will be calculated based on study drug accountability data.

No formal statistical testing is planned. Descriptive statistics for the level of on-treatment adherence with the number and percentage of subjects belonging to adherence categories ($< 75\%$, ≥ 75 to $< 90\%$, $\geq 90\%$) will be provided.

By-subject listing of study drug administration and drug accountability will be provided separately by subject ID number (in ascending order) and visit (in chronological order).

4.3. Protocol Deviations

Subjects who did not meet the eligibility criteria for study entry, but enrolled in the study will be summarized. No exemptions will be granted for this study. The summary will present the number and percentage of subjects who did not meet at least 1 eligibility criterion and the number of subjects who did not meet specific criteria by treatment group based on the All Randomized Analysis Set. A by-subject listing will be provided for those subjects who did not meet at least 1 eligibility (inclusion or exclusion) criterion. The listing will present the eligibility criterion (or criteria if more than 1 deviation) that subjects did not meet and related comments, if collected.

Protocol deviations occurring after subjects entered the study are documented during routine monitoring. The number and percentage of subjects with important protocol deviations by deviation reason will be summarized by treatment group in the Randomized and OL Phases for the All Randomized Analysis Set and OL Safety Analysis Set respectively. A by-subject listing will be provided for those subjects with any important protocol deviation.

5. BASELINE CHARACTERISTICS

5.1. Demographics

Subject demographic variables (ie, age, sex, race, and ethnicity) will be summarized by treatment group and overall for each study phase using descriptive statistics for age, and using number and percentage of subjects for sex, race, and ethnicity. Age in the Randomized/OL Phase summary is calculated in years at the date of first study drug administration in the Randomized/OL Phase. The summary of demographic data will be provided for the Safety Analysis Set and OL Safety Analysis Set, respectively.

A by-subject demographic listing, including the informed consent date, will be provided by subject ID number in ascending order for the All Randomized Analysis Set.

5.2. Other Baseline Characteristics

For the Randomized Phase, baseline characteristics include:

- Fibrosis stage score (fibrosis stages according to the NASH CRN classification and Ishak method will be summarized separately)
- Hepatic collagen content
- NAS
- Steatosis grade
- Lobular inflammation grade
- Hepatocellular ballooning grade
- ALT
- AST
- GGT
- ALP
- Total bilirubin
- Direct bilirubin
- INR
- Platelets

- MELD score
- Child-Pugh (CP) score
- Height
- Body weight
- Body mass index (BMI) as a continuous variable and as categories (18 to < 25 kg/m², 25 to <30 kg/m² and ≥ 30 kg/m²)
- Diabetes mellitus (absence or presence)
- Fasting glucose
- HbA1c
- ELF test score
- Fibrosis-4 (FIB-4) index
- NAFLD Fibrosis Score (NFS)
- Liver stiffness by transient elastography
- Use of Vitamin E
- History of SVR to therapy for chronic HCV

Use of Vitamin E is defined as treatment with Vitamin E on Day 1. Sustained virologic response is defined as HCV antibody positive and HCV virus negative at baseline.

For the OL Phase, baseline characteristics include:

- ALT
- AST
- GGT
- ALP
- Total bilirubin
- INR
- Platelets

- Body weight
- BMI as a continuous variable and for categories ($< 18 \text{ kg/m}^2$ [if applicable], $18 \text{ to } < 25 \text{ kg/m}^2$, $25 \text{ to } < 30 \text{ kg/m}^2$ and $\geq 30 \text{ kg/m}^2$)
- Fasting glucose
- HbA1c

All baseline characteristics will be summarized by treatment group and overall for the Safety Analysis Set and OL Safety Analysis Set as defined in Section 3.2. Descriptive statistics for continuous variables and number and percentage of subjects for categorical variables will be used. No formal statistical testing is planned.

A by-subject listing of baseline characteristics will be provided by subject ID number in ascending order for the All Randomized Analysis Set.

5.3. Medical History

General medical history data will be collected at Screening. General medical history data will be coded using the current version of the Medical Dictionary for Regulatory Activities (MedDRA). System organ class (SOC), high-level group term (HLGT), high-level term (HLT), preferred term (PT), and lower-level term (LLT) will be provided in the medical history dataset.

6. EFFICACY ANALYSES

Efficacy analyses will include data collected in the Randomized Phase only. All data on or after the first dose of OL study drug will be excluded from efficacy analyses.

6.1. Primary Histology Efficacy Endpoint

6.1.1. Definition of Primary Histology Efficacy Endpoint

The primary histology efficacy endpoint at Week 48 is the proportion of subjects who achieve a ≥ 1 -stage improvement in fibrosis (according to the NASH CRN classification) without worsening of NASH (defined as a ≥ 1 point increase in hepatocellular ballooning or lobular inflammation).

6.1.2. Statistical Hypothesis for Primary Histology Efficacy Endpoint

The statistical hypotheses to be tested can be stated as:

$$H_{S0i}: \delta_{si} = 0 \text{ versus } H_{SAi}: \delta_{si} \neq 0, i = 1 \text{ or } 2$$

Where δ_{s1} (δ_{s2}) is the difference in the proportion of subjects who achieve a ≥ 1 -stage improvement in fibrosis without worsening of NASH at Week 48 between SEL 18 mg (or SEL 6 mg) and placebo. The hypotheses will be tested in the FAS with $\alpha = 0.025$ for the comparison between each SEL arm and the placebo arm. The study will evaluate if each SEL arm performs better (ie, has a higher proportion of subjects who achieve a ≥ 1 -stage improvement in fibrosis without worsening of NASH) than the placebo arm.

6.1.3. Analysis of Primary Histology Efficacy Endpoint

A stratified Mantel-Haenszel (MH) test will be used to compare the differences in proportions of subjects who achieve a ≥ 1 -stage improvement in fibrosis without worsening of NASH at Week 48 between SEL 18 mg (SEL 6 mg) and placebo, adjusting for the presence or absence of diabetes mellitus at baseline and ELF test score ≥ 9.76 or < 9.76 at baseline. Subjects with missing data regarding fibrosis stage and NAS elements used to define worsening of NASH (hepatocellular ballooning and lobular inflammation) at Week 48 will be analyzed as treatment failures for this endpoint. The 2-sided 95% CIs for the difference in proportions between SEL 18 mg (SEL 6 mg) and placebo will be constructed based on stratum-adjusted MH proportions as follows {Koch 1989}:

$$p_A - p_B \pm Z_{(1-\alpha/2)} * SE(p_A - p_B),$$

where

- $(p_A - p_B) = \frac{\sum w_h d_h}{\sum w_h}$, is the stratum-adjusted MH proportion difference, where $d_h = p_{Ah} - p_{Bh}$ is the difference in the proportion of subjects who achieved a ≥ 1 -stage improvement in fibrosis without worsening of NASH between SEL 18 mg (SEL 6 mg) and placebo in stratum h.

- $w_h = \frac{n_{Ah}n_{Bh}}{n_{Ah} + n_{Bh}}$, is the weight based on the harmonic mean of sample size per treatment group for each stratum where n_{Ah} and n_{Bh} are the sample sizes of SEL 18 mg (SEL 6 mg) and placebo in stratum h.

- $SE(p_A - p_B) = \sqrt{\frac{\sum w_h^2 \left[\frac{p_{Ah}^*(1-p_{Ah}^*)}{n_{Ah}-1} + \frac{p_{Bh}^*(1-p_{Bh}^*)}{n_{Bh}-1} \right]}{(\sum w_h)^2}}$, where

$$p_{Ah}^* = \frac{m_{Ah} + 0.5}{n_{Ah} + 1} \text{ and } p_{Bh}^* = \frac{m_{Bh} + 0.5}{n_{Bh} + 1}, \text{ and}$$

m_{Ah} and m_{Bh} are the number of subjects who achieved a ≥ 1 -stage improvement in fibrosis without worsening of NASH in SEL 18 mg (SEL 6 mg) and placebo in stratum h.

- $\alpha = 0.05$ for the calculation of 95% CI
- $Z_{(1-\alpha/2)} = Z_{0.975} = 1.96$ is the 97.5th percentile of the normal distribution
- $Z \text{ score} = \frac{(p_A - p_B)}{SE(p_A - p_B)}$

If the computed lower confidence bound is less than -1 , the lower bound is defined as -1 . If the computed upper confidence bound is greater than 1 , then the upper bound is defined as 1 .

The point estimates, 95% CIs, and corresponding p-values based on Z tests for the differences in proportions, and the 95% CIs for proportion of responders in each treatment group based on the Clopper-Pearson method will be calculated.

A logistic regression analysis will also be performed to assess the odds ratio between each of the SEL arms and the placebo arm, adjusting for stratification factors. The point estimate of the odds ratio, 95% CIs of odds ratio, and corresponding p-values for each SEL arm versus the placebo arm will be reported.

Forest plots of the treatment differences in the proportion of subjects who achieved primary histology endpoint will be generated for the subgroup analyses as described in Section 3.4 and sensitivity analyses as described in Section 3.6.1, respectively.

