1.2. Study Design

This is a Phase 3, randomized, double-blind, placebo-controlled study evaluating the safety and efficacy of SEL in subjects with NASH and bridging (F3) fibrosis.

The overall study design is presented graphically in [Figure 1-1](#).

Figure 1-1. Overall Study Design

- EOT = end of treatment; ET = early termination; PTM = Placebo-to-Match

Subjects meeting the study’s entry criteria were randomly assigned in a 2:2:1 ratio to 1 of 3 treatment groups: Group A, Group B and Group C, respectively, as shown in [Figure 1-1](#). Randomization was stratified by the presence or absence of diabetes mellitus (determined by medical history or based on Screening laboratory values if previously undiagnosed [ie, hemoglobin A1c (HbA1c) \geq 6.5% or fasting plasma glucose \geq 126 mg/dL]) and by Enhanced Liver Fibrosis (ELF™) test score \geq 9.76 or $<$ 9.76 during Screening. Study drugs will be administered for up to a total of 240 weeks.

Subjects who experience a clinical event (except all-cause mortality and liver transplantation) prior to completing the Week 240 Visit of the Randomized Phase will be offered the option to rollover into an Open-Label (OL) Phase for a total treatment duration of 240 weeks inclusive of the Randomized Phase. Rollover into the OL Phase of the study must occur within 60 days of confirmation of the event. Subjects starting the OL Phase of the study will complete the same study procedures as during the Randomized Phase of the study, **CCI**

The schedule of assessments is provided as an appendix to this analysis plan ([Appendix 1](#)).

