1.3. Sample Size and Power

With a sample size of 320 subjects in each active treatment arm and 160 subjects in the placebo arm, the study has 94% power to detect a difference in the proportion of subjects with a ≥ 1 -stage improvement in fibrosis without worsening of NASH of 15% or more at Week 48 at a significance level of 0.025 (2-sided), assuming the proportion of subjects that meet the endpoint in the placebo arm is 12%.

With regard to the clinical efficacy endpoint, subjects will be followed for a period of up to 240 weeks. The estimate of the expected event rate is 30% in untreated patients, producing an expected EFS rate of 70% at 240 weeks in the placebo arm. SEL is expected to improve the EFS rate to 83.7% (expected event rate of 16.3%) compared with placebo (hazard ratio (HR), 0.50). We also expect a 20% overall dropout rate. Given the above assumptions, for comparison of the SEL arms versus the placebo arm, together with a total sample size of 800 subjects (2:2:1 ratio), and assuming the log-rank test statistic is evaluated using a 2-sided 0.025 significance level, the study will have 85% power to evaluate the superiority of each SEL arm versus placebo with respect to EFS.

Therefore, the overall power for the trial, assuming independence between the primary efficacy endpoint and clinical efficacy endpoint, is 80% ($94\% \times 85\%$). It should be noted that this is a lower bound estimate as these 2 endpoints are expected to be positively correlated.

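### The Week 48 analysis is valid and adequately powered, but also adjusting for baseline ballooning, lobular inflammation and collagen could add modest precision at almost no cost

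*SAP*

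**What the plan says.** SAP 6.1.1 defines a responder as a subject whose NASH CRN fibrosis stage falls by at least one without worsening of NASH. Worsening means at least a one-"point increase in hepatocellular ballooning or lobular inflammation".

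SAP 6.1.3 compares each SEL arm with placebo by a stratified MH difference, "adjusting for the presence or absence of diabetes mellitus at baseline and ELF test score" category, which gives four strata. The supporting logistic regression is fitted "adjusting for stratification factors", so it has the same two factors. SAP 3.3 sets that rule for efficacy endpoints generally. The imputation model in SAP 3.6.1 uses treatment and the same two factors.

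SAP 5.2 lists "Hepatic collagen content", lobular inflammation grade and hepatocellular ballooning grade among the baseline characteristics. No unredacted efficacy text uses them as covariates.

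**The concern.** Two of the three omitted variables are the reference values for half of the endpoint. A subject at the top of a grade scale cannot worsen on it, while a subject at grade 1 can, and Protocol 4.2 requires at least grade 1 on each at entry. Fibrosis stage cannot serve as a covariate because every eligible subject is F3. Collagen content is the listed quantitative measure that can differ within F3, and Protocol 1.2.7.3.1.4 describes collagen reduction as consistent with stage improvement in the Phase 2 study.

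The Week 48 test decides whether an arm proceeds to EFS, and failure in both arms ends the trial (SAP 3.5). Placebo has only 160 subjects, so a chance imbalance in baseline histology is possible and would go unadjusted. If these variables predict response beyond diabetes and ELF, the planned analysis is less precise than it could be with data already listed for collection.

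**Working it through.** **Inputs from SAP 1.3.** "With a sample size of 320 subjects in each active treatment arm and 160 subjects in the placebo arm"; placebo response 12%; difference 15 points (27% v 12%); two-sided alpha 0.025 per arm, so z = 2.2414; stated power 94%. Missing Week 48 histology counts as failure (SAP 6.1.3), so the analysed number is not reduced.

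**Step 1: reproduce the plan's power, with no covariate gain.**

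- Pooled rate = (160 × 0.12 + 320 × 0.27) / 480 = 0.22.
- Null SE = √[0.22 × 0.78 × (1/160 + 1/320)] = 0.0401.
- Alternative SE = √[0.12 × 0.88/160 + 0.27 × 0.73/320] = 0.0357.
- Power = Φ[(0.15 − 2.2414 × 0.0401) / 0.0357] = 95.4%.
- With continuity correction ½(1/160 + 1/320) = 0.0047 subtracted from the difference, power = 94.0%.

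The stated 94% is reproduced.

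**Step 2: what a prognostic covariate would buy.** Let R² be the share of outcome variance that baseline histology explains beyond diabetes and ELF. Both SEs are multiplied by √(1 − R²). The documents give no R², so this is a range.

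| Assumed R² | SE ratio | Power, 12% v 27% (pooled) |
|---|---|---|
| 0 | 1.000 | 95.4% |
| 0.02 | 0.990 | 95.8% |
| 0.05 | 0.975 | 96.3% |
| 0.10 | 0.949 | 97.2% |
| 0.15 | 0.922 | 97.9% |

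**Step 3: simulation of the SAP's own Z against an adjusted logistic likelihood-ratio test** (320 v 160, four strata, one normal baseline score). Assumed log-odds slopes of 0.5 / 0.8 / 1.1 give AUC 0.64 / 0.71 / 0.77.

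| | SAP Z | Adjusted |
|---|---|---|
| 12% v 27% | about 96.5% | 96.6 / 97.3 / 98.5% |
| 12% v 23% (assumed; not in the plan) | about 80% | 81 / 82 / 85% |

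A repeat with two pure-noise covariates added to the adjusted model gave 96.6 / 97.1 / 98.4% against about 96%, and 79.4 / 81.9 / 83.3% against about 79%. The ratio of unadjusted to adjusted variance was 1.03–1.04 / 1.08 / 1.13–1.16. The largest corresponds to a variance cut of 1 − 1/1.16 = 13.8%. With uninformative histology the ratio was 1.00, and power was 95.3% adjusted against 95.9%, and 77.7% against 78.8%.

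**Step 4: simulation with ordinal grades and a continuous collagen score, using a standardised logistic risk difference** (1,500 trials per setting; Monte Carlo error about √(0.96 × 0.04/1500) = 0.5 points). The covariate distributions are assumed.

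| R², placebo / active | SD, MH v adjusted | Power, MH v adjusted |
|---|---|---|
| about 0 (uninformative) | 0.0358 v 0.0358 | 95.8 v 96.3% |
| 0.015 / 0.026 | 0.0348 v 0.0348 | 96.6 v 96.7% |
| 0.051 / 0.084 | 0.0360 v 0.0350 | 95.9 v 97.3% |
| 0.107 / 0.159 | 0.0361 v 0.0340 | 96.1 v 98.3% |

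The last row is a variance ratio of (0.0361/0.0340)² = 1.13, a cut of about 11%. A further run of this kind gave ratios of 0.99–1.00 (uninformative), 1.01–1.02 (weak) and 1.06–1.09 (moderate).

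**Step 5: the grades as extra MH strata.** With two ballooning and three inflammation grades assumed, there are 4 × 6 = 24 strata, or about 160/24 ≈ 7 placebo subjects each. The mean SE rises from about 0.0365 to 0.0415 and power falls to about 92–94%. About two strata per trial are unusable because an arm has fewer than two subjects and the n − 1 denominator or the weight fails.

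**Step 6: level.** In the SEL-favouring tail (nominal 1.25%), the adjusted likelihood-ratio test rejected in 1.2–1.4% of null trials in one run and 1.4–1.7% in the other. The SAP Z gave about 1.4–1.6% and 1.6–1.9%.

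**The case against.** The strongest reply is that this is a preference. Prespecified MH adjustment for the randomisation factors is valid, matches the design and delivers the stated power. That stands. A reader might infer that the primary test is defective or underpowered, but Step 1 shows otherwise.

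A reader might also take the endpoint to be a change from all three variables. It is not. Collagen is not an endpoint component, F3 is constant by eligibility, and only the no-worsening clause uses baseline grades. The ceiling argument gives a direction for that clause alone. The documents do not show how baseline grade relates to fibrosis improvement.

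Some within-F3 variation may already be captured. SAP Appendix 7 lists ELF as a noninvasive fibrosis marker, and Protocol 1.3 links the 9.76 cut to liver-related events. What counts is histology's value beyond ELF, which no document gives. The loss of precision is therefore conditional.

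Nor is the change free. Step 5 shows that the planned MH formula cannot absorb the grades, so a gain needs a different estimator. Replacing the primary test would also depart from the MH test named in Protocol 8.6.1 and the synopsis. SAP 3.6.1 pools the primary method by Rubin's rule, which needs an estimate and SE, and it applies non-responder imputation (NRI) with or without a baseline value. These points shape the fix but do not remove the case for a prespecified adjusted analysis.

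The exploratory efficacy sections are redacted and may use baseline histology, so nothing is inferred from their absence.

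**Conclusion.** The point holds as a modest, conditional gain in efficiency. It is not an error in the plan. Over the assumed prognostic range, adjustment cuts the variance of the risk difference by roughly 0 to 14%. It adds about 0 to 2 power points at the design effect and about 0 to 5 if the true rates were 12% v 23%. If the histology is uninformative, the cost is about a point of power or less, close to simulation error.

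These figures rest on assumed prognostic strengths and covariate distributions, and on 320 v 160 analysed subjects. The documents do not support the stronger reading that the plan gives up known precision for nothing. They do support prespecifying the adjustment now: the covariates are already listed at baseline, and the same analysis added after unblinding would be post hoc.

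**What to change.** Before the Week 48 unblinding, in SAP 6.1.3:

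- Prespecify a logistic model with arm, the two stratification factors, baseline ballooning and lobular inflammation grades as ordinal scores, and log collagen content. Use a missing-indicator for any missing baseline histology, so that every FAS subject is kept under NRI.
- Report the standardised risk difference with its CI. Supply its estimate and SE for Rubin pooling in the multiple-imputation and tipping-point analyses.
- At minimum, put these covariates into the logistic regression already planned and keep the stratified MH test as primary.
- If the adjusted analysis becomes primary, align Protocol 8.6.1 and the synopsis and keep MH as supportive. Check the level of the chosen test (likelihood-ratio or Wald) by simulation, and state in SAP 6.3.2 whether the secondary endpoints, which reuse the 6.1.3 test, follow.
- Do not add the grades as MH strata.

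The minimum version costs SAP wording and a little programming, with no new data. The fuller version also needs the protocol text aligned, and the primary estimate becomes model-based.
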